**Statistical Analyses Plan (SAP):**

Data will be imported to R statistical software and the distributions will be examined visually to make a decision about the appropriate statistical tests (i.e. parametric / non-parametric) to be used for all comparisons. All statistical analyses will be conducted using R statistical software. Family-wise error rate will be maintained at 0.05.

Free living EI and saturated fat intake during main three meals (i.e. breakfast, lunch and dinner) of each subject will be determined using RFPM and the meals of all test subjects will be categorized based on the presence or the absence of eggs in the meals. Means of EI and saturated fat intake during each main meal will be compared between the two categories (i.e. eggs present vs. eggs absent) using multi-level mixed-effects regression models constructed using the lmerTest package in R statistical software. Age, sex, baseline BMI and / or waist circumference will be included in the models as subject-level covariates.

Based on RFPM data, mean EI and saturated fat intake of the high egg consumers (i.e. individuals in the top quartile based on egg consumption) will be compared with the mean EI and saturated fat intake of the low egg consumers (i.e. individuals in the bottom quartile based on egg consumption) via Welch t-tests or the Wilcoxon test, depending on the distributions of the data.

Linear regression models will be constructed to examined the associations between a) total EI, b) saturated fat intake and c) egg intake and each of i) baseline insulin level, ii) blood glucose level, iii) HOMA-IR, and iv) HbA1C level. The usual regression assumptions will be assessed and any concerns will be ameliorated as appropriate (e.g. apply a transformation as guided by Box-Cox)

Using the data obtained in the randomized partial crossover trial, multi-level mixed effects regression models will be constructed using the lmerTest package in R statistical software to predict each of a) PYY (AUC and pre-post change); b) GLP-1 (AUC and pre-post change); c) ghrelin (AUC and pre-post change); d) blood glucose (AUC and pre-post change); e) insulin (AUC and pre-post change); f) metabolic rate using i) the presence of eggs in the diet; ii) the

presence of a high content of saturated fat in the diet; iii) their interaction. Age, sex, baseline BMI and / or waist circumference will be included in the models as subject-level covariates.

Mean EI estimates of food records and 24-hour recall methods will be compared with the EI estimates of RFPM both with and without controlling for age, sex, baseline BMI and / or waist circumference by constructing a mixed-effects regression model to predict EI using the lmerTest package in R statistical software. The methods of estimation will be included in the model as a categorical independent variable and RFPM will be specified as the reference category. Age, sex, baseline BMI and / or waist circumference will be included in the models as subject-level covariates.

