## **B. Hypotheses:**

These aims will test the following hypotheses:

1. Meals that include eggs will have higher energy and saturated fat contents as determined by RFPM, compared to corresponding meals (i.e. breakfast, lunch, or dinner) without eggs.
2. As determined by RFPM, individuals of the study sample who will be in the highest quartile in terms of egg consumption in the free-living condition (defined as high egg consumers) will have a higher intake of saturated fat and total energy as compared to individuals who will be in the lowest quartile in terms of egg consumption (defined as low egg consumers).
3. Baseline insulin level, blood glucose level, the Homeostatic Model Assessment (HOMA) index of insulin resistance using fasting glucose and insulin levels, and HbA1C will be positively associated with total EI and saturated fat intake determined by RFPM, even when adjusted for age, sex, BMI and waist circumference
4. Above outcome variables will not be associated with egg intake determined by RFPM.

5. In the randomized partial crossover study, presence of eggs in the breakfast will be associated with a) a greater increase (i.e. both area under the curve and pre-post change) in satiety hormones (i.e. PYY and GLP-1), b) a less profound increase in blood glucose and insulin levels, c) a greater decrease in the hunger hormone (ghrelin) and d) an increase in the area under the curve of metabolic rate when controlled for the content of saturated fat in the test diets.
6. In the randomized partial crossover study, presence of a high amount of saturated fat in the breakfast will be associated with a) a greater increase (i.e. both area under the curve and pre-post change) in satiety hormones (i.e. PYY and GLP-1), b) a less profound increase in blood glucose and insulin levels, c) a greater decrease in the hunger hormone (ghrelin) and d) an increase in the area under the curve of metabolic rate when controlled for the presence of eggs in the test diets.
7. In the randomized partial crossover study, the associations mentioned in hypothesis 5 will be moderated by the presence of a high amount of saturated fat in the diet.
8. Estimates of total EI by RFPM will be significantly greater than EI estimates by 7-day food record and the 24-hour recall in dietary assessment.

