1. Meals that include eggs have higher energy and saturated fat content vs similar meals without eggs.
2. The daily total energy and saturated fat intakes are different between low and high egg consumers.
3. The HbA1C levels are positively associated with total energy intake or saturated fat intake.
4. When adjusted for age, body mass index (BMI), waist circumference, energy and saturated fat intake, HbA1c is not significantly associated with egg intake.

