**Statistical procedures:**

**a. Power calculations:** With 40 subjects, we will be at least 80% powered to detect effect sizes that are equal to or greater than 0.45, which is a fairly modest effect size, using a nominal value of 0.05 for the level of each test. We will similarly be powered to detect a correlation with magnitude of at least 0.43; see Figure 1. With conservative adjustment for multiple comparisons, these thresholds rise to 0.61 and 0.53, respectively; see Figure 2.

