**Figure 1:**

**Figure 2:**

**b. Analyses:**

- Within-subject comparison of meals that include eggs vs similar meals (e.g. breakfast vs breakfasts) without eggs for energy and saturated fat content.
- Comparison of daily energy and saturated fat intakes between low and high egg consumers (top quartile vs bottom quartile as determined by FFQ). Because this measure of egg consumption is

based on self-reported FFQ recall, as a sensitivity analysis we will also consider the correlations between these outcomes and observed egg consumption over the period of observation.

iii. Correlation between HbA1C or fasting glucose levels and total energy intake or saturated fat intake (for 7 days), with and without adjustment for age, BMI, energy and saturated fat intake.

**Expected results:** We expect that meals, particularly breakfasts, that include eggs have higher energy and saturated fat content due to accompanying foods (such as hash browns, fries, sausages, or bacon). This may further contribute to greater overall energy and saturated fat intake for high egg consumers vs those who consume eggs less frequently. Finally, we anticipate that when adjusted for age, BMI, energy and saturated fat intake, fasting blood glucose or HbA1c will not be significantly associated with egg intake.

**Implications:** we expect that the purported association of eggs to dysregulated glycemic control is independent of eggs, but mainly due to the dietary pattern around egg intake. If true, an informational campaign will be needed to clear eggs from the “guilt by association”. However, if egg intake is indeed associated with impaired glycemic control, then appropriate steps should be taken to inform people accordingly.

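### Read plainly, the SAP's family-wise rule also covers the egg-intake regressions of Hypothesis 4, where a smaller alpha makes the predicted finding of no association easier to reach

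*Combined protocol and SAP*

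**What the plan says.** The first paragraph of the Statistical Analyses Plan deals with the choice of tests for all comparisons and ends: "Family-wise error rate will be maintained at 0.05". It names no family and no method, and it exempts no hypothesis.

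The same section then plans the regressions that bear on Hypothesis 4: "Linear regression models will be constructed to examined the associations between a) total EI, b) saturated fat intake and c) egg intake". The outcomes are four baseline measures, namely insulin, glucose, HOMA-IR and HbA1c. That is 3 exposures by 4 outcomes, or 12 associations, 4 of which have egg intake as the exposure.

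Under B. Hypotheses, Hypothesis 3 predicts positive associations of these outcomes with energy and saturated fat intake. Hypothesis 4 predicts the reverse for eggs: "Above outcome variables will not be associated with egg intake determined by RFPM". No equivalence margin, confidence-interval criterion or power statement accompanies it.

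The 40-subject proposal appended to the protocol has related text. Its fourth hypothesis says that after adjustment "HbA1c is not significantly associated with egg intake", and its expected results say that "fasting blood glucose or HbA1c will not be significantly associated with egg intake". Its power paragraph gives detectable values of 0.45 (effect size) and 0.43 (correlation) at a nominal 0.05 per test, and adds: "With conservative adjustment for multiple comparisons, these thresholds rise to 0.61 and 0.53, respectively".

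**The concern.** Family-wise control lowers the per-test alpha to limit false claims that something is associated or different. That suits hypotheses supported by rejecting a null. Hypothesis 4 is supported by not rejecting one. With no other criterion stated, the p-value threshold is the only decision rule a reader can apply to it, and lowering that threshold helps the predicted result. An adjustment that is conservative for the other hypotheses is anti-conservative for this one.

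At stake is whether a real association between egg intake and a glycaemic measure is reported as absent. The Summary expects to show that glucose alterations are independent of eggs, and the Significance section looks ahead to dietary recommendations.

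**Working it through.** **Inputs.** N = 48 (Overview of the study design); family-wise 0.05 (SAP); 4 egg tests among 12 regression tests (SAP). From the appended power paragraph: N = 40, 80% power, detectable correlation 0.43 unadjusted and 0.53 adjusted, effect size 0.45 and 0.61. Assumed, because the documents are silent: two-sided tests, Bonferroni alpha = 0.05/m, and the value of m.

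**Formula.** With s = atanh(r) × √(n − 3) and c the two-sided critical value at alpha = 0.05/m, P(non-significant) = Φ(c − s) − Φ(−c − s). With k covariates, n − 3 becomes n − 3 − k.

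**Step 1: the documents' own figures (N = 40).**
- r = 0.43: s = 0.460 × √37 = 2.80. Power at alpha 0.05 is Φ(2.80 − 1.96) ≈ 79.9%, so the stated 0.43 is reproduced.
- d = 0.45: power by a paired t-test is 79.3%, which also matches.
- Adjusted values: m = 9 gives 79.3% power at r = 0.53 and 81.4% at d = 0.61; m = 10 gives 78.3% and 80.4%. The correlation figure alone implies alpha of about 0.006 (m ≈ 8). The stated shift thus corresponds to roughly 8 to 10 tests.
- At a true r of 0.43, the chance of non-significance goes from 20% unadjusted to 48% with m = 8 and 49% with m = 9.

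**Step 2: the current sample size (N = 48, no covariates).** For r = 0.30, s = 0.3095 × √45 = 2.076. Unadjusted: Φ(1.960 − 2.076) = Φ(−0.116) = 45.4%. With m = 4 (alpha 0.0125): Φ(2.498 − 2.076) = Φ(0.421) = 66.3%. The other entries follow in the same way.

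| Family assumed | True r 0.20 | True r 0.30 | True r 0.40 |
|---|---|---|---|
| Unadjusted | 72.5% | 45.4% | 18.9% |
| m = 4 (egg tests only) | 87.2% | 66.3% | 36.5% |
| m = 9 (fits the appended figures) | 92.1% | 75.7% | 47.2% |
| m = 12 (all regressions) | 93.4% | 78.5% | 50.9% |
| m = 55 (a count of all SAP tests) | 97.5% | 89.3% | 68.3% |

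The count of 55 is 6 meal, 2 quartile, 12 regression, 33 crossover and 2 method comparisons.

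**Step 3: covariates.** With 4 covariates (age, sex, BMI and waist circumference, as in Hypothesis 3), the r = 0.30 figures become 49.1% unadjusted, 69.7% (m = 4), 78.6% (m = 9) and 81.1% (m = 12). The pattern is unchanged.

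**Step 4: what this does to an observed result.** At N = 48 the smallest significant correlation is 0.284 unadjusted, 0.356 with m = 4 and 0.403 with m = 12. An observed correlation of 0.35 would count as an association unadjusted and as non-significant under any of these families.

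**Step 5: what the correction does protect.** With four independent tests at 0.05 and no true association, the chance of at least one false positive is 1 − 0.95⁴ = 18.5%.

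**The case against.** Several points on the other side are sound.

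- **Coverage is inferred.** A reader might conclude that the SAP expressly applies the correction to Hypothesis 4. It does not: the sentence states no scope, and correction within each hypothesis or analysis would also fit it. Coverage is the plain reading of an unrestricted sentence. Even a family of only the four egg tests gives 66% at r = 0.30.
- **The appended power paragraph does not settle it.** One might read its adjusted correlation as proof that the adjustment was meant for egg intake against glycaemia. But it belongs to a 40-subject proposal of different design, and the correlations in that proposal's analysis list do not include that pair. Its not-significantly-associated wording is not in the current Hypothesis 4 either. These figures illustrate the direction and do not establish the current plan's alpha.
- **The case for eggs does not rest on this test alone.** These regressions are in neither outcome list. Glucose and insulin after the test breakfasts are primary outcomes of randomised Part II, and Hypotheses 1 to 3 also feed the argument.
- **The correction is not pointless here.** One might infer that Hypothesis 4 should simply leave the family. But the appended proposal says people should be informed if egg intake is associated with impaired glycaemic control, so a rejection would support a public claim. Full exemption would give up protection against a false one (18.5% in step 5).
- **Other methods bite less.** A step-down procedure would have a smaller effect than Bonferroni, and an added test need not always lower the threshold for the egg tests. It would not reverse the direction: no family-wise adjustment at 0.05 makes a test easier to reject than at unadjusted 0.05.

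What survives is that nothing in the plan stops a multiplicity-adjusted, non-significant result from being reported as no association.

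**Conclusion.** The concern holds in a limited form. On the plain reading of the SAP, the family-wise rule covers the four egg-intake regressions, and there it raises the error that matters for a claim of no association. At N = 48 and a true correlation of 0.30, the chance of non-significance goes from 45% to about 66%, 76% or 79% for families of 4, 9 or 12. This assumes Bonferroni, two-sided Fisher-z tests and no covariates. The direction is firm; the size is a range because family and method are unstated.

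The correction aggravates a weakness that is already there. At unadjusted 0.05 a true correlation of 0.20 is still missed 72.5% of the time, so removing the correction would not make non-significance evidence of no association. The documents do not support saying that the rule guards only against the wrong error, or that the study's conclusion about eggs depends on these regressions alone.

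**What to change.** Add to the opening paragraph of the SAP:

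> Multiplicity-adjusted p-values are used only for claims that an association or difference exists, including any claim that egg intake is associated with a glycaemic measure. Each Hypothesis 4 egg-intake coefficient is also reported with its unadjusted 95% confidence interval. Any statement that eggs are not associated with glycaemia is based on the range of associations that this interval excludes, and never on a non-significant p-value, adjusted or unadjusted.

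Apply the same rule to secondary outcome 6 (HbA1c in high versus low egg consumers), which addresses the same question.

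The change needs no new data or subjects, and it keeps the protection against falsely implicating eggs. Its cost is that a conclusion of no association becomes harder to state, because the intervals will be wide. If the observed correlation were exactly 0, the unadjusted 95% interval at N = 48 would be ±tanh(1.96/√45) = ±0.284, so correlations up to about 0.28 in either direction could not be excluded.

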### **Outcome Measures:**

#### **A. Primary Outcome Measures:**

1. Difference of energy intake (kcal) in meals containing eggs as compared to meals that do not contain eggs

Energy intake will be determined using Remote Food Photography Method (RFPM) and the meals of all test subjects will be categorized based on the presence or the absence of eggs in the meals.

[Time Frame: Day 1-7 of the ecological momentary assessment part (Part I) of the study]

2. Difference of energy intake (kcal) in high egg consumers as compared to low egg consumers  
Comparison of mean daily energy intake as measured by Remote Food Photography Method (RFPM) between high egg consumers and low egg consumers identified by providing a food frequency questionnaire (FFQ).

[Time Frame: Day 1-7 of the ecological momentary assessment part (Part I) of the study]

3. Difference of saturated fat (g) intake in meals containing eggs as compared to meals that do not contain eggs

Saturated fat intake will be determined using Remote Food Photography Method (RFPM) and the meals of all test subjects will be categorized based on the presence or the absence of eggs in the meals.

[Time Frame: Day 1-7 of the ecological momentary assessment part (Part I) of the study]

4. Difference of saturated fat (g) intake in high egg consumers as compared to low egg consumers

Comparison of saturated fat intake as measured by Remote Food Photography Method (RFPM) between high egg consumers and low egg consumers identified by providing a food frequency questionnaire (FFQ).

[Time Frame: Day 1-7 of the ecological momentary assessment part (Part I) of the study]

5. Difference of blood glucose levels compared between different test breakfasts

This will be measured on visit 1 and 2 after providing test breakfasts.

[Time Frame: Changes in concentration (area under the curve; AUC) from 30 minutes prior to breakfast to 180 minutes after consumption of test breakfasts (Part II of the study)]

6. Difference of insulin levels compared between different test breakfasts

This will be measured on visit 1 and 2 after providing test breakfasts.

[Time Frame: Changes in concentration (area under the curve; AUC) from 30 minutes prior to breakfast to 180 minutes after consumption of test breakfasts (Part II of the study)]

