Several issues question the applicability of the epidemiological observations about egg consumption and diabetes. While eggs improve glycemic control of diabetic individuals under the controlled environment of experimental intervention [11], epidemiological studies indicate that under free living conditions, higher egg intake predicts risk of diabetes or CVD risk for diabetic individuals. Possibly, higher egg intake is simply a marker for other dietary indiscretions. For instance, from lowest to highest egg consumers, men reported greater daily energy intake from 1,870 kcal to 2,372 kcal, greater saturated fat intake and a 5-fold increase in bacon consumption, although their BMIs were nearly identical [3] - this strongly suggests that greater egg intake is associated with greater intake of other nutrients. Predictably, the association of CVD with egg consumption disappeared when bacon intake was also considered [3]. ***Individuals predisposed to impaired glycemic control*** may be particularly susceptible to undesirable health effects of higher saturated fat and energy intake. In such individuals, saturated fat may overwhelm the beneficial effects of eggs on lipid and glycemic profile. A possibility that beneficial effects of eggs on lipids can get counterbalanced is also expressed by Hu et al. [3]. For a clearer understanding in those with impaired glycemic control, the effect of eggs should be separated from that of accompanying saturated fat consumed.

Therefore, our ***Central hypothesis*** is that the association of egg intake with increased CVD risk in diabetics, or with greater risk of developing diabetes, is due to the accompanying dietary pattern, and not due to eggs per se. Specifically, we postulate that rather than eggs, the greater energy intake and saturated fat intake (e.g. bacon, butter, hash browns, etc.) associated with ***greater*** egg consumption contribute to the stated health risks. We propose to test this hypothesis as follows, by using the remote food photography method (RFPM), which was developed and validated by our co-investigator (CM). RFPM employs smartphone technology as a means of estimating energy intake remotely from participants' home environments.

**Aim: Use the RFPM to accurately determine the dietary pattern associated with egg intake in 40 free living non-diabetic individuals who eat eggs often.**

This aim will test the following hypotheses:

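### The SAP does not say whether the egg-meal coefficient for primary outcomes 1 and 3 is a within-person contrast; read in the usual way, it is partly mixed with the between-person contrast of outcomes 2 and 4

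*Combined protocol and SAP*

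**What the plan says.** Under Primary Outcome Measures, outcomes 1 and 3 are differences in energy and saturated fat between meals with and without eggs, where "the meals of all test subjects will be categorized based on the presence or the absence of eggs in the meals". Hypothesis 1 expects egg meals to be higher "compared to corresponding meals (i.e. breakfast, lunch, or dinner) without eggs". It matches on meal type and does not say that the comparison is within the same person.

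The SAP states: "Means of EI and saturated fat intake during each main meal will be compared between the two categories (i.e. eggs present vs. eggs absent". The model for this is described only as a multi-level, mixed-effects one fitted in R. On adjustment, the SAP adds: "Age, sex, baseline BMI and / or waist circumference will be included in the models as subject-level covariates". It gives no model formula, no random-effects structure, no centring and no term for how often a participant eats eggs.

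Hypothesis 2 predicts that people in the top quartile of egg consumption "will have a higher intake of saturated fat and total energy as compared to individuals who will be in the lowest quartile". Primary outcomes 2 and 4 test this.

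The appended earlier proposal, written for 40 subjects, describes the meal analysis under Statistical procedures as "Within-subject comparison of meals that include eggs vs similar meals (e.g. breakfast vs breakfasts) without eggs for energy and saturated fat content". The current SAP, for 48 subjects, does not carry that wording over.

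**The concern.** Frequent egg eaters supply most of the egg meals, and infrequent eaters supply most of the others. If frequent eaters also eat more at every meal, a comparison of egg with non-egg meals shows a difference even when no individual's egg meals differ from that person's own non-egg meals. A random intercept removes much of this, but removes all of it only if egg frequency is unrelated to usual intake. Hypothesis 2 predicts that the two are related.

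The listed covariates may not break the link. The appended proposal's Background cites a cohort in which, from lowest to highest egg consumption, "men reported greater daily energy intake from 1,870 kcal to 2,372 kcal", and reports that BMI hardly differed across those groups.

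At stake is the interpretation of two primary outcomes. The study's argument is that foods eaten alongside eggs raise the energy and saturated fat of those meals. That is a question about meals within a person, and the planned coefficient may answer it only in part.

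**Working it through.** **The plan's own figure.** The current SAP gives no power for outcomes 1 and 3. The appended proposal claims at least 80% power with 40 subjects for an effect size of 0.45 at a 0.05 level. A two-sided paired t-test (noncentrality 0.45 × √40 = 2.85, 39 df) gives 79.3%. A two-sample test gives 28% for 20 v 20 and 16% for 10 v 10. The figure therefore fits a within-subject contrast, in line with that proposal's wording.

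**Inputs from the documents.** 48 subjects; 7 days, so up to 7 meals of each main type (m = 7); cited daily gap 2,372 − 1,870 = 502 kcal.

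**Assumptions.** The gap is split evenly over three main meals: 502 / 3 = 167 kcal, taken as the difference between the top and bottom egg-consumption quartiles. Per-meal SD is 250-350 kcal, the egg share of one meal type is 35%, the intake ICC is 0.2-0.5 and the ICC of the egg indicator (stability of egg habits) is 0.2-0.4. The true within-person effect is zero.

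**Weight on the between-person effect.** In a random-intercept model the egg coefficient equals w × between + (1 − w) × within, where

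- ψ = (1 − ICC) / (1 − ICC + m × ICC), using the intake ICC;
- B = mρ + 1 − ρ and W = (m − 1)(1 − ρ), with ρ the egg-habit ICC; these are the between- and within-subject sums of squares of the indicator per subject, up to a common factor;
- w = ψB / (W + ψB).

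Example with intake ICC 0.2 and ρ = 0.2: ψ = 0.8 / 2.2 = 0.364, B = 2.2, W = 4.8, so w = 0.8 / 5.6 = 0.143.

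**Bias.** A 167 kcal quartile gap corresponds to a slope of 305 kcal per unit of egg-meal probability at ρ = 0.2 and 219 at ρ = 0.4. Seven meals measure that probability imperfectly, with reliability mρ / B: 1.4 / 2.2 = 0.636 and 2.8 / 3.4 = 0.824. The observed between-person slopes are therefore about 194 and 180. Bias is w times this slope; in the example, 0.143 × 194 = 28 kcal. Because bias is proportional to the gap, half the gap gives half the bias. The standard error of the within-person estimate exceeds that of the planned one by the factor 1 / √(1 − w).

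The simulated columns come from 800 REML fits per setting; each range covers SD 350 and 250.

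| ρ | Intake ICC | w | Bias, formula (kcal) | Bias, simulated | False positives, simulated | Bias at half gap, formula | SE increase |
|---|---|---|---|---|---|---|---|
| 0.2 | 0.2 | 0.143 | 28 | 26-29 | 10-18% | 14 | 8% |
| 0.2 | 0.3 | 0.103 | 20 | 21-23 | 9-13% | 10 | 6% |
| 0.2 | 0.5 | 0.054 | 10 | 10-11 | 6-7% | 5 | 3% |
| 0.4 | 0.2 | 0.256 | 46 | 46-48 | 20-37% | 23 | 16% |
| 0.4 | 0.3 | 0.191 | 34 | 32-34 | 12-21% | 17 | 11% |
| 0.4 | 0.5 | 0.106 | 19 | 19-21 | 10-14% | 10 | 6% |

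**Sensitivity.**

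- SD 300 kcal and 30% egg meals: 12-53 kcal and 7-30% false positives at the full gap; 7-25 kcal and 5-12% at half.
- SD 300 kcal and egg share about 22-30%: 8-36 kcal and 6-18% at the full gap; 5-17 kcal and 5-8% at half; 5-6% false positives at a quarter.
- Extreme case, intake ICC 0.1 with ρ = 0.4: up to 70 kcal and 64%.
- All 21 main meals in one model: w is 3-11% at intake ICC 0.2-0.3, against 10-26% with 7 meals.

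**With the egg term split.** Across all REML settings, the within-person coefficient averaged −3.4 to +3.9 kcal against a truth of zero, and its false-positive rate was 3.6-7.0%, around the nominal 5%.

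**The case against.** The strongest reply is that the criticised model is partly inferred. The SAP says mixed-effects and no more; an analyst could centre the indicator and still comply. This stands, and it is why the point is that the contrast is unspecified, not that a wrong model is written down.

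Second, the current protocol never defines outcomes 1 and 3 as within-person. A reader might infer that the SAP breaks a binding definition. It does not: the only within-subject wording is in the appended 40-subject proposal, which shows earlier intent.

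Third, the 167 kcal gap may be too large here. It comes from men in a cited cohort. This trial excludes people eating less than one egg a week, and its food frequency questionnaire starts at twice weekly, so the range of egg intake may be narrower. Some of the gap belongs to snacks. Some may come from foods eaten with eggs, which is a genuine meal-level effect. Age and sex, which are in the planned model, were not simulated and could absorb part of it. All of this stands, and it means the bias could be negligible.

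Fourth, a reader might infer that outcomes 1 and 3 merely repeat outcomes 2 and 4. That does not follow: in the settings tabulated the between-person weight is 5-26%, so the coefficient is mostly within-person.

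None of this removes the mechanism. No listed covariate carries habitual egg intake, and the protocol's own Hypothesis 2 predicts the correlation that produces the bias.

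**Conclusion.** The concern holds as partial contamination of an unspecified contrast. Under the ordinary random-intercept reading with one uncentred egg indicator, the coefficient for outcomes 1 and 3 blends within- and between-person effects, and Hypothesis 2 gives the direction: towards finding egg meals higher.

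The direction is firm if Hypothesis 2 is true; the size is not. With no true within-person effect and 7 meals per type, bias is roughly 10-50 kcal per meal and the false-positive rate about 6-30% at a 167 kcal gap, higher in extreme settings. At half that gap the figures are about 5-25 kcal and 5-12%. They depend on the per-meal SD, intake ICC, stability of egg habits, share of egg meals, and how much of the cited gap applies to main meals in this sample. The documents give none of these. Saturated fat (outcome 3) shares the mechanism but was not quantified.

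The change is worth making because it is cheap and removes the ambiguity whatever the true size.

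**What to change.** Amend the SAP before analysis. Within each meal type:

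- Enter the egg indicator minus the participant's own mean, plus that mean (the participant's proportion of egg-containing meals) as a subject-level covariate.
- Name the within-person coefficient as the test of primary outcomes 1 and 3, and report the between-person coefficient separately.
- State the random-effects structure.
- Report how many participants have both egg and non-egg meals of that type, since only they inform the within-person estimate. In the REML simulations 19-39% of participants had only one kind.

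The cost is one extra covariate and a few SAP sentences, with no new data. The standard error grows by roughly 2-20%, more when egg habits are stable.
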